## 5.4.9 Storage

All study drugs should be kept in a secure place under appropriate storage conditions. The investigational product label on the bottle and the Investigator Brochure specifies the appropriate storage.

## 5.4.10 Management of toxicity of olaparib

Any toxicity observed during the course of the study could be managed by interruption of the dose of study treatment or dose reductions. Repeat dose interruptions are allowed as required, for a maximum of 4 weeks on each occasion, until improved Hb  $\geq$ 10 g/dl. If the interruption is any longer, the study team must be informed. Upon recovery, study treatment can be dose reduced to 250 mg twice daily as a first step and to 200 mg twice daily as a second step in the case of repeat Hb decrease. If the reduced dose of 200 mg twice daily is not tolerable, no further dose reduction is allowed and study treatment should be discontinued.

Once dose is reduced, escalation is not permitted.

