## 5.4.11 Management of hematological toxicity

## 5.4.11.1 Management of anemia

Table 2 Management of anemia

Hemoglobin	Action to be taken
Hb < $10 \ but \ge 8 \ g/dl$ (CTCAE Grade 2)	Give appropriate supportive treatment and investigate causality. Investigator judgement to continue olaparib with supportive treatment (eg transfusion) or interrupt dose for a maximum of 4 weeks.
	If repeat Hb< 10 $but \ge 8$ g/dl, dose interrupt (for max of 4 weeks) until Hb $\ge 10$ g/dl and upon recovery dose reduction to 250 mg twice daily as a first step and to 200 mg twice daily as a second step may be considered.
Hb < 8 g/dl (CTCAE Grade 3)	Give appropriate supportive treatment (e.g. transfusion) and investigate causality.
(	Interrupt olaparib for a maximum of 4 weeks. until improved to $Hb \ge 10$ g/dl.
	Upon recovery dose reduce to 250 mg twice daily as a first step and to 200 mg twice daily as a second step in the case of repeat Hb decrease.

Common treatable causes of anemia (e.g., iron, vitamin B12 or folate deficiencies and hypothyroidism) should be investigated and appropriately managed. In some cases management of anemia may require blood transfusions. For cases where patients develop prolonged hematological toxicity (≥2 week interruption/delay in study treatment due to CTC grade 3 or worse anemia and/or development of blood transfusion dependence), refer to Section 6.7.1.3 for the management of this.

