#### 5.4.11.2 Management of neutropenia, leukopenia and thrombocytopenia

Table 3 Management of neutropenia, leukopenia and thrombocytopenia

Toxicity	Study treatment dose adjustment
CTCAE Grade 1-2	Investigator judgement to continue treatment or if dose interruption, this should be for a maximum of 4 weeks; appropriate supportive treatment and causality investigation
CTCAE Grade 3-4	Dose interruption until recovered to CTCAE gr 1 or better for a maximum of 4 weeks. If repeat CTCAE grade 3-4 occurrence, dose reduce olaparib to 250 mg twice daily as a first step and 200 mg twice daily as a second step

Adverse event of neutropenia and leukopenia should be managed as deemed appropriate by the investigator with close follow up and interruption of study drug if CTC grade 3 or worse neutropenia occurs.

Primary prophylaxis with Granulocyte colony stimulating factor (G-CSF) is not recommended, however, if a patient develops febrile neutropenia, study treatment should be

stopped and appropriate management including G-CSF should be given according to local hospital guidelines. Please note that G-CSF should not be used within at least 24 h (7 days for pegylated G-CSF) of the last dose of study treatment unless absolutely necessary.

Platelet transfusions, if indicated, should be done according to local guidelines.

For cases where patients develop prolonged hematological toxicity (≥2 week interruption/delay in study treatment due to CTC grade 3 or worse), refer to Section 6.7.1.3.

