## 5.4.12 Management of non-hematological toxicity

Repeat dose interruptions are allowed as required, for a maximum of 4 weeks on each occasion. If the interruption is any longer than this the study monitor must be informed. Where toxicity reoccurs following re-challenge with study treatment, and where further dose interruptions are considered inadequate for management of toxicity, then the patient should be considered for dose reduction or must permanently discontinue study treatment.

Study treatment can be dose reduced to 250 mg bid as a first step, and to 200 mg bid as a second step. Treatment must be interrupted if any NCI-CTCAE grade 3 or 4 adverse event occurs which the investigator considers to be related to administration of study treatment.

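### Section 5.4.10 covers any toxicity but sets only a haemoglobin end point for interruptions, which contradicts Table 3 and is not reconciled with Table 2 or Section 5.4.12

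*Combined protocol and SAP*

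**What the plan says.** Section 5.4.10 sets its scope in its first sentence: "Any toxicity observed during the course of the study could be managed by interruption of the dose of study treatment or dose reductions". The next sentence reads "Repeat dose interruptions are allowed as required, for a maximum of 4 weeks on each occasion, until improved Hb" and gives the level as 10 g/dl or above. After recovery the dose may go to 250 mg twice daily, then to 200 mg twice daily "as a second step in the case of repeat Hb decrease".

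The sections that follow treat toxicities by class:

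- **Table 2 (Section 5.4.11.1, anaemia).** At a first haemoglobin of 8 to below 10 g/dl, the investigator may continue olaparib with supportive treatment or interrupt it. At a repeat value in that range, or at any value below 8 g/dl, dosing is interrupted until haemoglobin is at least 10 g/dl.
- **Table 3 (Section 5.4.11.2, neutropenia, leukopenia and thrombocytopenia).** For grade 3-4 events the rule is "Dose interruption until recovered to CTCAE gr 1 or better for a maximum of 4 weeks". The dose steps follow a repeat grade 3-4 event.
- **Section 5.4.12 (non-haematological toxicity).** A hold beyond the cap has to be reported to the monitor; the rule begins "Repeat dose interruptions are allowed as required, for a maximum of 4 weeks on each occasion. If the interruption is any longer than this". On severe events linked to olaparib it adds: "Treatment must be interrupted if any NCI-CTCAE grade 3 or 4 adverse event occurs which the investigator considers to be related". Both dose steps are available.
- **Section 5.4.12.1 (pulmonary symptoms).** Restart is possible if CT shows no abnormality, symptoms resolve and the investigator judges it appropriate.

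**The concern.** A section addressed to all toxicities should either hold for all of them or send the reader to the section that does. Section 5.4.10 does neither. Its recovery condition and its second-step trigger are both haemoglobin conditions, and they carry no information about a low neutrophil count, vomiting or fatigue.

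What is at stake is the clarity and uniform application of a safety instruction. When dosing may resume after an interruption, and what triggers a lower dose, should not depend on which of two neighbouring sections the investigator opens first. The situation is foreseeable. Table 1 lists neutropenia, leukopenia, thrombocytopenia, dyspnoea, vomiting, diarrhoea, nausea and fatigue as common at grade 3 or above.

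**Working it through.** No sample size, power or event count enters this point, so the check sets the passages side by side.

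| Toxicity | Section 5.4.10 | Class-specific section | Agreement |
|---|---|---|---|
| Anaemia, Hb below 8, or repeat Hb 8 to below 10 g/dl | Resume at Hb 10 g/dl or above | Table 2: same level | Yes |
| Anaemia, first Hb 8 to below 10 g/dl | Interruption, if used, ends at Hb 10 g/dl or above | Table 2: olaparib may continue, at investigator judgement | Not reconciled |
| Other cytopenias, grade 3-4 | Hb 10 g/dl or above; second step on a repeat Hb fall | Table 3: grade 1 or better; steps on repeat grade 3-4 | Contradiction |
| Non-haematological, related grade 3-4 | Hb 10 g/dl or above; second step on a repeat Hb fall | Section 5.4.12: must interrupt; no Hb condition and no restart condition; both steps open | Not reconciled |
| Pulmonary | Hb 10 g/dl or above | Section 5.4.12.1: clear CT and symptoms resolved | Contradiction |

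**Where the wording fits.** Table 2 labels haemoglobin of 8 to below 10 g/dl as grade 2, so 10 g/dl or above lies outside grade 2. For anaemia needing interruption, Section 5.4.10 and Table 2 name the same level. The phrase about a repeat haemoglobin fall also stands in the row of Table 2 for values below 8 g/dl. The interruption sentence in Section 5.4.12 is nearly the same as that in Section 5.4.10, with the haemoglobin clause absent. The text of Section 5.4.10 therefore reads as anaemia wording under a general heading.

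**What Section 5.4.12 leaves open.** It requires a stop for related grade 3-4 events and foresees re-dosing ("Where toxicity reoccurs following re-challenge with study treatment"). Its general text does not say what state the event must have reached first. Section 5.4.12.2, on nausea and vomiting, adds none.

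**Two illustrations of the conflict, not of what would happen:**

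1. Grade 3 neutropenia with haemoglobin 13 g/dl. The end point in Section 5.4.10 is met on the day of interruption. Table 3 requires recovery to grade 1 or better.
2. Related grade 3 vomiting, now resolved, with a first haemoglobin of 9.5 g/dl. Section 5.4.10 read literally continues the hold. Table 2 lets olaparib continue at that haemoglobin. Section 5.4.12 sets no haemoglobin condition.

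**The case against.** The best defence is that the specific section governs. Section 5.4.12 has its own interruption sentence, Table 3 has its own recovery grade, and Section 5.4.10 is permissive in tone. A sensible investigator would use haemoglobin for anaemia only. That is a fair account of likely practice, but no sentence says that the class-specific sections override Section 5.4.10, whose first sentence claims every toxicity. The conflict stands.

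The defence does defeat several stronger readings that a reader might infer:

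- **That haemoglobin is the only written restart condition outside anaemia.** Table 3 and Section 5.4.12.1 state others, and Section 5.4.12 has an interruption rule free of haemoglobin.
- **That the plan lets an unresolved grade 3-4 event be re-dosed.** Section 5.4.12 requires interruption for related events of that grade. Section 5.4.10 makes what follows conditional on recovery. Section 5.4.12.3 sets its own interruptions apart from those for toxicity resolution. What remains is narrower: outside pulmonary events, no restart condition is stated in Section 5.4.12.
- **That a recovered man with haemoglobin below 10 g/dl must stay off drug.** This is one reading of conflicting sections, and Table 2 points the other way at a first value of 8 to below 10 g/dl.
- **That the wording changes who is replaced or analysed.** With surgery on Day 90 and dosing to the day before, about 89 dosing days are planned. One full 4-week hold takes 28 (28/89 = 31%) and leaves 89 - 28 = 61 days, or 61/7 = 8.7 weeks, above the 6-week replacement threshold in Section 5.8. The 4-week cap is the same in Section 5.4.10, Tables 2 and 3 and Section 5.4.12, so the length of a maximum hold does not come from the haemoglobin clause. Section 3.2 allows breaks for toxicity, so a permitted hold is not shown to remove a man from the efficacy set in Section 11.1.1.

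Frequency should not be overstated either. Table 1 gives categories, not rates, and covers completed olaparib studies generally. Section 1.5 describes myelosuppression, nausea and vomiting in advanced prostate cancer as grade 1 or 2.

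**Conclusion.** The point holds as an internal contradiction in an operative safety section. Followed literally, Section 5.4.10 gives a wrong cross-reading for every toxicity other than anaemia. It contradicts Table 3 on both the recovery condition and the dose-step trigger, and it contradicts the pulmonary criterion in Section 5.4.12.1. It is unreconciled with Table 2 at a first haemoglobin of 8 to below 10 g/dl and with the general text of Section 5.4.12.

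Its size is textual. The documents give no rate from which to compute how often an investigator would meet the conflict, and no effect on the sample size, the primary comparison, replacement or the analysis sets is shown. The conclusion rests on reading the sentences as printed and on the absence of any stated order of precedence between the general and specific sections. It takes no position on which clinical criterion is right. It deserves correction because the contradiction concerns when dosing resumes, and the repair is cheap.

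**What to change.** The sponsor and investigator should reconcile Section 5.4.10, Tables 2 and 3 and Section 5.4.12 (with 5.4.12.1). For each toxicity class (anaemia, other cytopenias, pulmonary, other non-haematological), the text should state which recovery condition ends an interruption and which event triggers each dose step. If restart for some class is meant to rest on investigator judgement, the text should say so. If the class-specific sections are meant to override Section 5.4.10, that should be stated too. Which criterion applies to which class is for the sponsor and investigator to decide.

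The cost is protocol wording only, handled under the amendment procedure in Section 8.5 if judged substantial. It adds no visits, tests or patients.

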## 5.4.11 Management of hematological toxicity

## 5.4.11.1 Management of anemia

Table 2 Management of anemia

Hemoglobin	Action to be taken
Hb < $10 \ but \ge 8 \ g/dl$ (CTCAE Grade 2)	Give appropriate supportive treatment and investigate causality. Investigator judgement to continue olaparib with supportive treatment (eg transfusion) or interrupt dose for a maximum of 4 weeks.
	If repeat Hb< 10 $but \ge 8$ g/dl, dose interrupt (for max of 4 weeks) until Hb $\ge 10$ g/dl and upon recovery dose reduction to 250 mg twice daily as a first step and to 200 mg twice daily as a second step may be considered.
Hb < 8 g/dl (CTCAE Grade 3)	Give appropriate supportive treatment (e.g. transfusion) and investigate causality.
(	Interrupt olaparib for a maximum of 4 weeks. until improved to $Hb \ge 10$ g/dl.
	Upon recovery dose reduce to 250 mg twice daily as a first step and to 200 mg twice daily as a second step in the case of repeat Hb decrease.

Common treatable causes of anemia (e.g., iron, vitamin B12 or folate deficiencies and hypothyroidism) should be investigated and appropriately managed. In some cases management of anemia may require blood transfusions. For cases where patients develop prolonged hematological toxicity (≥2 week interruption/delay in study treatment due to CTC grade 3 or worse anemia and/or development of blood transfusion dependence), refer to Section 6.7.1.3 for the management of this.

#### 5.4.11.2 Management of neutropenia, leukopenia and thrombocytopenia

Table 3 Management of neutropenia, leukopenia and thrombocytopenia

Toxicity	Study treatment dose adjustment
CTCAE Grade 1-2	Investigator judgement to continue treatment or if dose interruption, this should be for a maximum of 4 weeks; appropriate supportive treatment and causality investigation
CTCAE Grade 3-4	Dose interruption until recovered to CTCAE gr 1 or better for a maximum of 4 weeks. If repeat CTCAE grade 3-4 occurrence, dose reduce olaparib to 250 mg twice daily as a first step and 200 mg twice daily as a second step

Adverse event of neutropenia and leukopenia should be managed as deemed appropriate by the investigator with close follow up and interruption of study drug if CTC grade 3 or worse neutropenia occurs.

Primary prophylaxis with Granulocyte colony stimulating factor (G-CSF) is not recommended, however, if a patient develops febrile neutropenia, study treatment should be

stopped and appropriate management including G-CSF should be given according to local hospital guidelines. Please note that G-CSF should not be used within at least 24 h (7 days for pegylated G-CSF) of the last dose of study treatment unless absolutely necessary.

Platelet transfusions, if indicated, should be done according to local guidelines.

For cases where patients develop prolonged hematological toxicity (≥2 week interruption/delay in study treatment due to CTC grade 3 or worse), refer to Section 6.7.1.3.

## 5.4.11.3 Management of prolonged hematological toxicities while on study treatment

If a patient develops prolonged hematological toxicity such as:

- ≥2 week interruption/delay in study treatment due to CTC grade 3 or worse anemia and/or development of blood transfusion dependence
- ≥2 week interruption/delay in study treatment due to CTC grade 3 or worse neutropenia (ANC < 1 x 10^9/L)
- ≥2 week interruption/delay in study treatment due to CTC grade 3 or worse thrombocytopenia and/or development of platelet transfusion dependence (Platelets < 50 x 10^9/L)

Check weekly differential blood counts including reticulocytes and peripheral blood smear. If any blood parameters remain clinically abnormal after 4 weeks of dose interruption, the patient should be referred to hematologist for further investigations. Bone marrow analysis and/or blood cytogenetic analysis should be considered at this stage according to standard hematological practice. Study treatment should be discontinued if blood counts do not recover to CTC gr 1 or better within 4 weeks of dose interruption.

Development of a confirmed myelodysplastic syndrome or other clonal blood disorder should be reported as an SAE and full reports must be provided by the investigator to AstraZeneca Patient Safety. Olaparib treatment should be discontinued if patient's diagnosis of MDS and/or AML is confirmed.

## 5.4.12 Management of non-hematological toxicity

Repeat dose interruptions are allowed as required, for a maximum of 4 weeks on each occasion. If the interruption is any longer than this the study monitor must be informed. Where toxicity reoccurs following re-challenge with study treatment, and where further dose interruptions are considered inadequate for management of toxicity, then the patient should be considered for dose reduction or must permanently discontinue study treatment.

Study treatment can be dose reduced to 250 mg bid as a first step, and to 200 mg bid as a second step. Treatment must be interrupted if any NCI-CTCAE grade 3 or 4 adverse event occurs which the investigator considers to be related to administration of study treatment.

## 5.4.12.1 Management of new or worsening pulmonary symptoms

If new or worsening pulmonary symptoms (e.g., dyspnea) or radiological abnormalities occur in the absence of a clear diagnosis, an interruption in study treatment dosing is recommended and further diagnostic workup (including a high resolution CT scan) should be performed to exclude pneumonitis.

Following investigation, if no evidence of abnormality is observed on CT imaging and symptoms resolve, then study treatment can be restarted, if deemed appropriate by the investigator. If significant pulmonary abnormalities are identified, these need to be discussed with the Study Physician.

## 5.4.12.2 Management of nausea and vomiting

Events of nausea and vomiting are known to be associated with olaparib treatment. In study D0810C00019 nausea was reported in 71% of the olaparib treated patients and 36% in the placebo treated patients and vomiting was reported in 34% of the olaparib treated patients and 14% in the placebo treated patients. These events are generally mild to moderate (CTCAE grade 1 or 2) severity, intermittent and manageable on continued treatment. The first onset generally occurs in the first month of treatment for nausea and within the first 6 months of treatment for vomiting. For nausea, the incidence generally plateaus at around 9 months, and for vomiting at around 6 to 7 months.

No routine prophylactic anti-emetic treatment is required at the start of study treatment, however, patients should receive appropriate anti-emetic treatment at the first onset of nausea or vomiting and as required thereafter, in accordance with local treatment practice guidelines. Alternatively, olaparib tablets can be taken with a light meal/snack (ie 2 pieces of toast).

As per international guidance on anti-emetic use in cancer patients (NCCN), generally a single agent antiemetic should be considered, e.g., dopamine receptor antagonist, antihistamines or dexamethasone.

## 5.4.12.3 Interruptions for intercurrent non-toxicity related events

Study treatment dose interruption for conditions other than toxicity resolution should be kept as short as possible. If a patient cannot restart study treatment within 4 weeks for resolution of intercurrent conditions not related to disease progression or toxicity, the case should be discussed with AZ study physician.

All dose reductions and interruptions (including any missed doses), and the reasons for the reductions/interruptions are to be recorded in the eCRF.

Study treatment should be stopped 1 day before prostatectomy. No stoppage of study treatment is required for any needle biopsy procedure.

Study treatment should be discontinued for a minimum of 3 days before a patient undergoes radiation treatment. Study treatment should be restarted within 4 weeks as long as any bone marrow toxicity has recovered.

Because the AEs related to olaparib may include asthenia, fatigue and dizziness, patients should be advised to use caution while driving or using machinery if these symptoms occur.

Table 4 Dose reductions for study treatment

Initial Dose	Following re-challenge post interruption: Dose reduction 1	Dose reduction 2
300mg twice daily	250mg twice daily	200mg twice daily

# 5.5 Concomitant and post-study treatment(s)

The use of any natural/herbal products or other traditional remedies should be discouraged, but use of these products, as well as use of all vitamins, nutritional supplements, and all other concomitant medications must be recorded in the case report form (CRF).

## Medications that may NOT be administered

No other anti-cancer therapy (chemotherapy, immunotherapy, hormonal therapy (Hormone replacement therapy (HRT) is acceptable), radiotherapy, biological therapy or other novel agent) is to be permitted while the patient is receiving study medication.

Live virus and live bacterial vaccines should not be administered whilst the patient is receiving study medication and during the 30 day follow up period. An increased risk of infection by the administration of live virus and bacterial vaccines has been observed with conventional chemotherapy drugs and the effects with olaparib are unknown.

#### Restricted concomitant medications

Strong or Moderate CYP3A inhibitors

Known strong CYP3A inhibitors (e.g., itraconazole, telithromycin, clarithromycin, boosted protease inhibitors, indinavir, saquinavir, nelfinavir, boceprevir, telaprevir) or moderate CYP3A inhibitors (ciprofloxacin, erythromycin, diltiazem, fluconazole, verapamil) should not be taken with olaparib.

If there is no suitable alternative concomitant medication then the dose of olaparib should be reduced for the period of concomitant administration. The dose reduction of olaparib should be recorded in the CRF with the reason documented as concomitant CYP3A inhibitor use.

- Strong CYP3A inhibitors reduce the dose of olaparib to 100mg bid for the duration of concomitant therapy with the strong inhibitor and for 5 half lives afterwards.
- Moderate CYP3A inhibitors reduce the dose of olaparib to 150mg bid for the duration of concomitant therapy with the moderate inhibitor and for 3 half lives afterwards.
- After the washout of the inhibitor is complete, the olaparib dose can be re-escalated.

